9.3. Populations for Analysis Sets

For the efficacy analyses in this study, the full analysis set (FAS) will be used according to the participants' assigned treatment to which they were randomized, regardless of the treatment they actually received. The FAS includes all randomized participants who receive at least one administration of study intervention. The FAS will be used for all efficacy analyses.

Safety analyses will include all participants who received at least 1 dose of study intervention and participants will be analyzed based on the treatment they actually received, regardless of the treatment groups to which they were assigned.

Pharmacokinetics analyses for bermekimab will include participants who receive at least one dose of bermekimab and have at least one post-dose sample collection. Antibodies to bermekimab will be analyzed for participants who receive at least one dose of bermekimab and have at least one post-dose sample collection.

9.4. Statistical Analyses

9.4.1. General Considerations

Efficacy and participant information analyses will include all randomized participants who received at least 1 dose of study intervention and will be analyzed based on the randomized treatment groups, regardless of the treatment they actually received.

Simple descriptive summary statistics, such as n, mean, standard deviation, median, inter quantile range, minimum, and maximum for continuous variables, and counts and percentages for discrete variables will be used to summarize most data.

In addition, treatment comparisons for binary endpoints will be performed using a Chi-Square test or Fisher's exact test in the case of rare events. For continuous efficacy endpoints, treatment comparisons will be performed using a mixed-effect model repeated measure (MMRM) model. The MMRM model includes treatment group, baseline value for the corresponding efficacy endpoint, visit, baseline value by visit, and treatment by visit interaction, if applicable. In addition, treatment differences and their associated 2-sided 90% confidence intervals (CIs) will be presented.

9.4.2. Primary Endpoint

The primary efficacy endpoint is the proportion of participants with EASI-75 at Week 16.

Primary Estimand: The primary estimand (ie, a precise definition of the primary targeted treatment effect) is defined by the following 5 attributes:

- **Population:** adult participants with moderate-to-severe AD
- **Variable/endpoint:** Binary response variable, where a responder is defined as a participant achieving an EASI-75 response at Week 16. A participant with an intercurrent event (ICE) in categories 1 to 3 defined below will be considered a non-responder.
- **Study intervention:**

Bermekimab 800 mg, 1200 mg, dose C mg IV qw

Placebo IV qw

- **Intercurrent Events:**

Table 4: Analysis Strategy for Addressing Intercurrent Events (ICEs)	
Intercurrent Events (ICEs)	Analysis Strategy for Addressing Intercurrent Events (ICEs)
1. Discontinuation of study intervention due to lack of efficacy, an AE of worsening of AD prior to Week 16 2. Initiation of a protocol-prohibited medication or therapy during the study that could improve AD prior to Week 16 3. Initiation of rescue medication for AD prior to Week 16	Composite Strategy: Participants with these intercurrent event are considered as EASI-75 non-responders after these events. The occurrence of these intercurrent event being captured in the variable definition.
4. Discontinuation of study intervention for reasons other than above defined reasons prior to Week 16	Treatment policy: Use observed data regardless of whether or not this intercurrent event had occurred

- **Population level summary:** Difference in the proportions of participants achieving an EASI-75 response at Week 16 between the bermekimab and placebo treatment groups.

Primary Endpoint Analysis

In the primary efficacy analysis, data from all randomized participants who received at least 1 administration of study intervention will be analyzed according to their assigned treatment group. The primary endpoint will be analyzed at Week 16 based on the primary estimand and the number and proportion of participants who achieve an EASI-75 response at Week 16 will be summarized for each treatment group. To address the primary objective, a Fisher's exact test at an alpha level of 0.1 will be used to compare each bermekimab group separately with placebo. The proportion difference between each bermekimab group and placebo group and its 2-sided 90% CI will be provided.

The study would be considered as positive if any of the comparisons for primary endpoint analysis (bermekimab 1200 mg vs placebo, and bermekimab C dose vs placebo) is less than or equal to p-value of 0.1. No formal statistical testing will be performed for the 800 mg vs placebo. For the analyses described above, participants with ICEs 1 through 3 before Week 16 will be considered as EASI-75 nonresponders at Week 16. For participants with ICE 4, observed data after this ICE will be utilized in the analysis. In addition, participants who do not return for evaluation or have missing components of EASI will also be considered as nonresponders at Week 16.

To examine the robustness of the primary endpoint analysis, additional analyses of the primary endpoint will be conducted using different data handling approaches; these analyses will be described in the SAP. To evaluate the consistency of the efficacy, subgroup analysis of the primary endpoint will be performed.

No adjustment for multiple comparisons will be made for primary endpoints.

Secondary Endpoints

The secondary analyses pertaining to efficacy are:

- The proportion of participants with both vIGA-AD 0 or 1 (on a 5-point scale) and a reduction from baseline of ≥ 2 points at Week 16 will be compared between each of the bermekimab groups and the placebo group.
- Proportion of participants with improvement (reduction) of eczema-related itch NRS ≥ 4 from baseline to Week 16 among participants with a baseline itch value ≥ 4 will be compared between each of the bermekimab groups and the placebo group.
- The proportion of participants with EASI-90 response at Week 16 will be compared between each of the bermekimab groups and the placebo group.

No adjustments for multiple comparisons will be made for the secondary endpoints.

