has received systemic immunosuppressant, immunomodulatory, or cytotoxic treatments (including, but not limited to, oral or injectable corticosteroids, cyclosporin, or methotrexate) that could affect AD or IGA evaluations within 4 weeks before the baseline visit, or any condition other than AD that, in the opinion of the investigator, is likely to require such treatment(s) within 4 weeks before the baseline visit.

26. has received natalizumab, belimumab, or agents that modulate B cells or T cells (eg, rituximab, alemtuzumab, abatacept, or visilizumab) within 12 months of the first administration of study intervention.

27. has received, or is expected to receive, any live virus or bacterial vaccination within 12 weeks before the first administration of study intervention. Non-live vaccines approved or authorized for emergency use (eg, COVID-19) by local health authorities are allowed.

28. has had a Bacille Calmette-Guerin (BCG) vaccination within 12 months prior to screening.

Prior/Concurrent Clinical Study Experience

29. has received any non-biologic investigational intervention (including investigational vaccines) within 30 days or 5 half-lives (whichever is longer) of any study intervention administration or is currently enrolled in another study using an investigational agent, device, or procedure

30. has known intolerance or hypersensitivity to any biologic medication, or known allergies or clinically significant reactions to murine, chimeric, or human proteins, mAbs, or antibody fragments.

31. is pregnant, or breast-feeding, or planning to become pregnant while enrolled in this study or within 12 weeks after the last dose of study intervention.

32. plans to father a child while enrolled in this study or within 12 weeks after the last dose of study intervention.

33. any condition for which, in the opinion of the investigator, participation would not be in the best interest of the participant (eg, compromise the well-being) or that could prevent, limit, or confound the protocol-specified assessments.

Diagnostic Assessments – Not applicable

Other Exclusions

34. employee of the investigator or study site, with direct involvement in the proposed study or other studies under the direction of that investigator or study site, as well as family members of the employees or the investigator

35. Criterion modified per Amendment 1

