6.8.3. Prohibited Therapies/Medications

The following therapies will not be allowed during the course of the study.

- Topical corticosteroids, except for rescue therapy (see Section 6.8.4, Rescue Medication)
- Topical calcineurin inhibitors (eg, tacrolimus and pimecrolimus)

- Topical phosphodiesterase inhibitors 4 (eg, crisaborole)
- Leukotriene inhibitors
- Allergen immunotherapy
- Phototherapy (including psoralen and UV-A, UV-B, tanning beds, and excimer laser)
- Bleach baths
- Systemic corticosteroids (oral)
 - A single course of oral systemic corticosteroids per standard of care for conditions other than AD, for a maximum of 10 days, will be allowed. The use of intramuscular (IM) and IV corticosteroid formulations is prohibited, and will lead to participant discontinuation of study intervention.
 - Other route of administration of corticosteroids including those inhaled, otic, ocular, nasal, or other routes of mucosal delivery of corticosteroids are allowed.
- Any systemic therapy, investigational or commercial (approved or off label use), used for the treatment of AD or symptoms of AD (eg, dupilumab)
- Topical and systemic janus kinase inhibitors
- Systemic immunosuppressant, cytotoxic, and immunomodulatory agents, including, but not limited to, methotrexate, azathioprine, cyclosporine, mycophenolate mofetil, and immunomodulatory biologic therapies (eg, guselkumab, risankizumab, secukinumab, rituximab, alemtuzumab, abatacept, or visilizumab)
- Any prescription topical treatment for AD, including prescription moisturizer, unless the prescribed moisturizer can be obtained OTC and it doesn't require a prescription.
- Interlukin-1 α inhibiting agents (eg, anakinra, rilonacept, canakinumab)
- Live vaccines, including BCG vaccine.

The sponsor must be notified in advance (or as soon as possible thereafter) of any instances in which prohibited therapies are administered.

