5.3. Primary Endpoint Analysis

5.3.1. Definition of Endpoint(s)

The primary efficacy endpoint is the proportion of patients achieving an EASI-75 response at Week 16. The EASI is a validated measure used in clinical practice and clinical trials to assess the severity and extent of AD. Four AD disease characteristics (erythema, thickness [induration, papulation, edema], [excoriation], and lichenification) will be assessed for severity by the investigator or designee on a scale of “0” (absent) through “3” (severe). In addition, the area of AD involvement will be assessed as a percentage by body area of head, trunk, arms, and legs and converted to a score of 0 to 6. In each body region, the area is expressed as 0, 1 (1% to 9%), 2 (10% to 29%), 3 (30% to 49%), 4 (50% to 69%), 5 (70% to 89%), or 6 (90% to 100%).

For each region, severity score is the sum of intensity for each of four signs.

- Severity score = Erythema + Edema/Papulation + Excoriation + lichenification intensity

For each region, multiple the severity score by the region score and by a multiplier. The multiplier is different for each body site.

- Head and neck: severity score x region score x 0.1
- Trunk: severity score x region score x 0.3
- Upper extremities: severity score x region score x 0.2
- Lower extremities: severity score x region score x 0.4

Add up the total scores for each region to determine the final EASI score. The minimum EASI score is 0 and the maximum EASI score is 72.

EASI-100 responder is defined as a 100% improvement from baseline in EASI total score (EASI score=0).

EASI-90 responder is defined as at least a 90% improvement from baseline in EASI total score.

EASI-75 responder is defined as at least a 75% improvement from baseline in EASI total score.

EASI-50 responder is defined as at least a 50% improvement from baseline in EASI total score.

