5.3.2. Analysis Methods for Primary Endpoint

Due to the early termination of the study, the primary endpoint of EASI-75 response at Week 16 will be listed. No formal analyses will be performed.

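### Does Table 4 need a row for the short oral corticosteroid course that section 6.8.3 permits?

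*Protocol*

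**What the plan says.** Protocol section 9.4.2, Table 4, names four intercurrent events. Events 1 and 4 are discontinuations of study intervention. Event 2 is "Initiation of a protocol-prohibited medication or therapy during the study that could improve AD prior to Week 16". Event 3 is the start of rescue medication for atopic dermatitis (AD). The text after the table adds that "participants with ICEs 1 through 3 before Week 16 will be considered as EASI-75 nonresponders at Week 16", and gives the same status to participants who do not return or whose EASI components are missing. After event 4, observed data are used.

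Section 6.8.3 lists oral systemic corticosteroids under its prohibited heading and then makes an exception: "A single course of oral systemic corticosteroids per standard of care for conditions other than AD, for a maximum of 10 days, will be allowed". For the other systemic routes it says: "The use of intramuscular (IM) and IV corticosteroid formulations is prohibited, and will lead to participant discontinuation of study intervention". Section 7.1 agrees, counting as prohibited corticosteroids only the IM and IV formulations and oral use beyond 10 days. Exclusion criterion 25 (section 5.2) bars "oral or injectable corticosteroids, cyclosporin, or methotrexate) that could affect AD or IGA evaluations within 4 weeks before the baseline visit".

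The SAP (5.3.1) states that "EASI-75 responder is defined as at least a 75% improvement from baseline in EASI total score", with no intercurrent-event rule. Its section 5.3.2 says that "the primary endpoint of EASI-75 response at Week 16 will be listed. No formal analyses will be performed". SAP section 1 and Appendix 2 give the reason: the sponsor ended the study early with few participants enrolled. SAP 5.5.2 lists EASI from Week 0 through Week 20, and SAP Appendix 5 provides a listing of concomitant medications.

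**The concern.** The primary estimand is presented as a full definition, yet it is silent on an event that the protocol itself foresees and permits. The permitted course is not prohibited therapy, not AD rescue and not a discontinuation, so no row applies. A participant whose Week 16 EASI was helped by a systemic steroid would be credited as a responder.

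This sits awkwardly beside two other rules. Criterion 25 treats oral corticosteroids as able to affect AD evaluations and protects the baseline end of the change score for 4 weeks, while nothing protects the Week 16 end. And starting topical rescue at any time before Week 16 makes a participant a non-responder, while a permitted systemic course in Week 15 does not.

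With only 12 pooled placebo participants planned, one such responder is 1/12 = 8.3 percentage points of the placebo rate, which could matter to a Fisher test at 0.1. Under the listings-only SAP the worry shrinks to interpretation: the SAP does not promise a marker for the course beside a listed EASI-75 responder.

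**Working it through.** **Step 1. Is the gap real?** Taking Table 4 row by row for a participant who takes the permitted course and stays on study intervention:

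- Events 1 and 4 need discontinuation: not met.
- Event 2 needs a prohibited therapy. Section 6.8.3 allows the course and section 7.1 leaves it out of the prohibited corticosteroids: not met.
- Event 3 needs rescue for AD. The course is for another condition: not met.
- The missing-data rule needs a missing Week 16 EASI: not met.

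The observed EASI is therefore used. In effect this is treatment policy, though the text does not say so.

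**Step 2. Reproduce the plan's power.** Inputs from Protocol section 9.2: 24 (1200 mg), 16 (dose C) and 12 (pooled placebo); 15% placebo; 65% or 70% active; Fisher's exact test at two-sided 0.1. Enumerating both binomials with 0.05 in each tail gives 85.1% for 24 vs 12 at 65% vs 15% (Table 3: 85%) and 86.1% for 16 vs 12 at 70% vs 15% (Table 3: 86%). The minimum-likelihood two-sided version gives 90.2% for the first row, so the per-tail version is used in step 4.

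**Step 3. How far can one case move the original test?** With the minimum-likelihood version:

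| Active | Placebo 2/12 | Placebo 3/12 |
|---|---|---|
| 16/24 | p = 0.012 | p = 0.033 |
| 11/16 | p = 0.009 | p = 0.054 |

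Near the planned rates, one extra placebo responder leaves the call at 0.1 unchanged. Averaged over possible outcomes, and given one such case in placebo, a significant result is lost in 5.9% to 14.8% of trials across the Table 3 rows (minimum-likelihood), or 9.1% to 19.3% (0.05 per tail). Given one such case in the active arm, a non-significant result becomes significant in 1.4% to 5.8%, or 2.2% to 6.3%. All of these presuppose that a case exists.

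**Step 4. Would counting users as non-responders do better?** The documents give no rate of use and no effect, so both are assumed, equal in the two arms: a share *u* takes the course near Week 16, and a share *q* of those who would otherwise fail then reach EASI-75.

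- As written, the observed rate is p + (1 − p)·u·q, so the difference between arms is (p₁ − p₀)(1 − u·q).
- With users as non-responders, the rate is p(1 − u), so the difference is (p₁ − p₀)(1 − u).

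Example with u = 5%, q = 50%, 65% vs 15%. As written: 0.65 + 0.35 × 0.025 = 65.9% and 0.15 + 0.85 × 0.025 = 17.1%, a difference of 50 × 0.975 = 48.75 points. As non-response: 0.65 × 0.95 = 61.75% and 0.15 × 0.95 = 14.25%, a difference of 47.5 points. Since q cannot exceed 1, the non-response rule never keeps more of the difference than the current text does. It can win on power only when q is large, because it also lowers the placebo rate.

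Power, 0.05 per tail:

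| Comparison | u | Non-response rule | As written, q = 25% | q = 50% | q = 100% |
|---|---|---|---|---|---|
| 24 vs 12, 65% vs 15% | 5% | 81.4% | 83.8% | 82.4% | 79.7% |
| 24 vs 12, 65% vs 15% | 10% | 77.4% | 82.4% | 79.7% | 74.1% |
| 16 vs 12, 70% vs 15% | 5% | 82.8% | 84.8% | 83.4% | 80.7% |
| 16 vs 12, 70% vs 15% | 10% | 79.2% | 83.4% | 80.7% | 75.4% |

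For 24 vs 12 at q = 75%, the current text gives 81.0% (u = 5%) and 76.9% (u = 10%), just under the non-response rule. The crossover therefore lies between 50% and 75% conversion.

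**Step 5. What does the current SAP do with the endpoint?** It lists EASI-75 status and tests nothing, so the effects in steps 3 and 4 do not arise.

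**The case for a change.** The strongest argument for a change is that an estimand should state its strategy for every foreseeable event rather than leave one to default, and that this default is at odds with the reasoning behind criterion 25. A case would not be far-fetched in the planned trial: at an assumed 2% or 5% use, the chance of at least one user among 60 is 1 − 0.98⁶⁰ = 70% or 1 − 0.95⁶⁰ = 95%, and among the 12 on placebo 21.5% or 46%. With few participants and no tests, individual responder status is also most of what the efficacy listings offer, and a marker would cost little.

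The first part stands as a remark on drafting: the strategy is implied, not written. It does not show that the implied strategy is wrong. Criterion 25 is a washout before baseline. It acknowledges that steroids can affect AD scores, but does not say how long a 10-day course affects a Week 16 EASI, so carrying its 4 weeks over to Week 16 would be an assumption.

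The marker argument is weaker. The SAP names the listings without fixing their columns, so the absence of a marker is not established, and concomitant medications are listed in any case. With few participants, reading the two listings together is easy. Nor is the point peculiar to steroids: the SAP's responder definition carries none of the Table 4 rules, so a marker for this course alone would leave rescue and prohibited therapy unmarked.

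**Conclusion.** Table 4 gives no stated strategy for the permitted oral course, and the observed Week 16 EASI is used by default. That default is reasonable for a therapy the protocol allows for another condition. Treating the course as non-response is a trade-off, not a correction: under equal use and effect in both arms it gives lower power unless well over half of would-be non-responders convert, and nothing in the documents supports an effect that large. If use differed between arms, the bias in the current handling could go either way, so its direction cannot be presumed.

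Writing the default down, or marking users in a listing, would make the record clearer but would change no result. The SAP plans no formal analysis, and the information needed to interpret a listed responder is already to be listed. The flip rates of 5.9% to 14.8% (or 9.1% to 19.3% with 0.05 per tail) apply only to the tests originally planned, and only if a steroid-assisted placebo responder occurs. No change to the plan is needed.

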5.1. Inclusion Criteria

Each potential participant must satisfy all of the following criteria to be enrolled in the study:

Age

1. ≥ 18 to ≤ 65 years (or the legal age of consent in the jurisdiction in which the study is taking place).

Type of Participant and Disease Characteristics

2. be otherwise healthy on the basis of physical examination, medical history, vital signs, and 12-lead electrocardiogram (ECG) performed at screening. Any abnormalities, must be consistent with the underlying illness in the study population and this determination must be recorded in the participant's source documents and initialed by the investigator.
3. have AD for at least 1 year (365 days) prior to the first administration of study intervention as determined by the investigator through participant interview and/or review of the medical history.
4. have a history of inadequate response to treatment for AD with topical medications or for whom topical treatments are otherwise medically inadvisable (eg, due to important side effects or safety risks).
5. have an EASI score ≥ 16 at screening and at baseline.
6. have an IGA score ≥ 3 at screening and at baseline.
7. have an involved BSA $\geq 10\%$ at screening and at baseline.

Sex and Contraceptive/Barrier Requirements

8. male or female (according to their reproductive organs and functions assigned by chromosomal complement)
9. all woman of childbearing potential must have a negative highly sensitive serum (β -human chorionic gonadotropin [β -hCG]) at pregnancy test at screening and a negative urine pregnancy test at Week 0 prior to administration of study intervention.

10. A woman must be (as defined in Section 10.5, Appendix 5: Contraceptive and Barrier Guidance)
 - a. Not of childbearing potential, OR

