8.1.1. Eczema Area and Severity Index (EASI)

The EASI is a validated measure used in clinical practice and clinical trials to assess the severity and extent of AD ([Hanifin 2001](#)). The EASI is a composite index with scores ranging from 0 to 72. Four AD disease characteristics (erythema, thickness [induration, papulation, edema], scratching [excoriation], and lichenification) will each be assessed for severity by the investigator or designee on a scale of “0” (absent) through “3” (severe). In addition, the area of AD involvement will be assessed as a percentage by body area of head, trunk, upper limbs, and lower limbs, and converted to a score of 0 to 6. In each body region, the area is expressed as 0, 1 (1% to 9%), 2 (10% to 29%), 3 (30% to 49%), 4 (50% to 69%), 5 (70% to 89%), or 6 (90% to 100%). The EASI will be collected at time points according to the SoA (Section [1.3](#)). See Section [10.10](#), Appendix 10: EASI for a representative example of the index.

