10.10. Appendix 10: Eczema Area and Severity Index (EASI)

EASI Score Calculation: Assessment is performed on the indicated body regions, with each component (erythema, induration/papulation, excoriation, lichenification) graded on a scale of 0 to 3 and summed. The component score is then multiplied by the area score corresponding to the degree of body area involvement, followed by the weighting factor for the particular body region. (diagram from francefoundation.com and table excerpted from [Hanifin 2001](#)). Below is a sample Score.

cation. The average degree of severity of each sign in each of the four body regions was assigned a score of 0 to 3 (none, mild, moderate, and severe, respectively) with half-steps allowed. It should be

Table 1. Eczema area and severity index: calculation for patients 8 years of age and older¹

Body region	EASI Score ^{2,3}
Head/Neck (H)	$(E+I+Ex+L) \times Area \times 0.1$
Upper limbs (UL)	$(E+I+Ex+L) \times Area \times 0.2$
Trunk (T)	$(E+I+Ex+L) \times Area \times 0.3$
Lower limbs (LL)	$(E+I+Ex+L) \times Area \times 0.4$
EASI =	Sum of the above 4 body region scores

¹For children aged 0–7 years, proportionate areas were head/neck, 20%; upper limbs, 20%; trunk, 30%; and lower limbs, 30%.

²E=—Erythema, I=—induration/papulation, Ex=—excoriation, L=—lichenification.

³Where area is defined on a 7-point ordinal scale: 0=—no eruption; 1=<10%; 2=<10%–29%; 3=<30%–49%; 4=<50%–69%; 5=<70%–89%; and 6=>90%–100%.

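### The primary non-responder rule covers any missing EASI component, so it overrides a 75% improvement that the recorded items already guarantee (minor)

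*Protocol*

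**What the plan says.** **Missing data.** Protocol 9.4.2 (Primary Endpoint Analysis) states that "participants who do not return for evaluation or have missing components of EASI will also be considered as nonresponders at Week 16". Neither document has another rule for a partly completed EASI.

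**Responder definition.** In the primary estimand of the same section, a responder is a participant who reaches EASI-75 at Week 16, overridden only by intercurrent events (ICEs) 1 to 3. SAP 5.3.1 agrees on the threshold: "EASI-75 responder is defined as at least a 75% improvement from baseline in EASI total score".

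**Scoring.** Under Protocol 8.1.1 the four signs "will each be assessed for severity by the investigator or designee on a scale of" 0 to 3, and area is scored 0 to 6 in each region. Appendix 10 adds: "The component score is then multiplied by the area score corresponding to the degree of body area involvement". SAP 5.3.1 has the same structure: "For each region, severity score is the sum of intensity for each of four signs", then, for example, "Head and neck: severity score x region score x 0.1".

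**Floor on baseline.** Participants must "have an EASI score ≥ 16 at screening and at baseline".

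**Status of the analysis.** After early termination, SAP sections 1, 5.3.2 and 6.2 replace all formal analysis with listings. SAP 5.3.1 does not restate the missing-component rule.

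**The concern.** An EASI form has 20 components: 4 signs in each of 4 regions, plus 4 area scores. Read literally, one blank among them at Week 16 makes the participant a non-responder. Non-responder imputation is meant for an unknown outcome. Because each EASI item is bounded, some incomplete forms leave the outcome fully known, and a blank item is not one of the ICEs that the estimand allows to override a response.

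At stake is the primary comparison in small groups. One reclassified participant moves the response rate by 1/24 = 4.2 points at 1200 mg, or 1/16 = 6.3 points at Dose C.

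**Working it through.** **1. Bounds from the scoring formula**

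Region score = (sum of 4 signs) x area x weight. The weights are 0.1 head/neck, 0.2 upper limbs, 0.3 trunk and 0.4 lower limbs. Response requires a Week 16 total of at most 0.25 x baseline. With baseline at least 16, that cut-off is never below 0.25 x 16 = 4.0.

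- One blank sign adds at most 3 x area x weight: 3 x 1 x 0.1 = 0.3 (head, area 1); 3 x 1 x 0.4 = 1.2 (lower limbs, area 1); 3 x 6 x 0.4 = 7.2 (lower limbs, area 6).
- At baseline 16 with one lower-limb sign blank at area 1, response is certain if the recorded items total at most 4.0 - 1.2 = 2.8.
- With the same blank at area 4, the bound is 3 x 4 x 0.4 = 4.8, above 4.0, so response cannot be certain at that baseline. Not every blank is harmless.

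**2. Worked example**

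- Baseline: sign sum 8 and area 3 in every region gives 8 x 3 x (0.1 + 0.2 + 0.3 + 0.4) = 24.0. The cut-off is 6.0.
- Week 16: head recorded as clear. In the other three regions area is 1 and the recorded signs sum to 3. Lower-limb lichenification is blank.
- Recorded total: 3 x 1 x (0.2 + 0.3 + 0.4) = 2.7.
- Worst case for the blank: 2.7 + 1.2 = 3.9, an improvement of (24.0 - 3.9)/24.0 = 83.8%.

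This participant is a certain EASI-75 responder, and 9.4.2 scores a failure.

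**3. The plan's power figures**

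Protocol Table 3 (SAP Table 1) gives 85% for 24 v 12 at 65% vs 15%, and 86% for 16 v 12 at 70% vs 15%. A continuity-corrected normal approximation at two-sided 0.10 gives 85.0% and 85.6%, and matches all nine rows to within 0.5 point. Exact enumeration of the stated two-sided Fisher test (p <= 0.10) gives 90.2% and 89.0%. Both methods are shown below.

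**4. Power under the rule**

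Let q be the share of true responders lost to the rule, equal in both arms. The documents do not give q; 0 to 10% is an assumed range. The rates become 0.65(1-q) or 0.70(1-q) against 0.15(1-q), and the difference shrinks by the factor (1-q): 50 points become 49.0 at 2% and 47.5 at 5%.

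| q | 24 v 12, exact Fisher | 24 v 12, Table 3 method | 16 v 12, exact Fisher | 16 v 12, Table 3 method |
|---|---|---|---|---|
| 0 | 90.2% | 85.0% | 89.0% | 85.6% |
| 2% | 89.1% | 83.3% | 87.8% | 83.9% |
| 5% | 87.3% | 80.7% | 85.8% | 81.2% |
| 10% | 83.7% | 75.9% | 82.2% | 76.4% |

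**5. Counts near the planned rates (two-sided Fisher)**

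- 16/24 v 2/12: p = 0.012. It takes five lost active responders to cross 0.10 (12/24 gives 0.076, 11/24 gives 0.143).
- 11/16 v 2/12: p = 0.009. It takes three (9/16 gives 0.054, 8/16 gives 0.114).

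A single loss matters only near the boundary, as between 9/16 and 8/16.

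**The case against.** Non-responder imputation is prespecified and conservative. Protocol 10.3.9 provides for investigator verification and data queries, and 10.3.11 for monitors comparing the eCRF with source, so lasting blanks should be uncommon. Section 9.4.2 also promises robustness analyses under other data handling. All of this stands and keeps the expected effect small. It does not remove the mismatch with the responder definition, and the SAP describes no such robustness analyses, having dropped formal analysis.

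A reader might infer three stronger points that the documents do not support:

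- **That any cleared region triggers the rule.** Area and each sign have an explicit score of 0, so a properly recorded clear region is complete. The problem arises there only if sites leave sign items blank when area is 0, on which both documents are silent.
- **That the loss falls only on active treatment, or is severe at Dose C.** The rule applies to both arms, and active-only loss would be a further assumption. Taking Dose C at 65% vs 15% also overstates the effect, because that scenario is not a Table 3 row; with 15% placebo, the Dose C rows start at 70%.
- **That the reported primary result is biased.** The SAP plans no test or estimated difference for EASI-75.

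**Conclusion.** The point holds as a minor defect in a stated rule. Some incomplete forms prove a 75% improvement, and 9.4.2 nevertheless scores those participants as non-responders, against its own estimand. The rule can only lower response rates; with equal proportional loss it also shrinks the treatment difference.

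The size rests on the assumed q. At 2% loss, power falls by about 1 point by exact Fisher and under 2 points by the Table 3 method. At 5%, both base scenarios stay above the 80% target under either method. At 10%, exact Fisher stays above 80% and the Table 3 method falls to about 76%. Nothing in the documents suggests a rate that high. These figures describe the protocol's planned analysis. What remains under the current SAP is the responder status shown in the listing for a partly completed form, which SAP 5.3.1 leaves undefined.

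**What to change.** Replace the missing-component clause in Protocol 9.4.2 with the following rule, and state it in SAP 5.3.1:

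1. A region with area score 0 scores 0, whether or not its sign items are filled.
2. For any other blank, set missing signs to 3 and missing areas to 6 and compute the total. Count the participant as a responder only if improvement from baseline is still at least 75% and none of ICEs 1 to 3 applies; otherwise as a non-responder.
3. A participant with no Week 16 EASI is a non-responder.

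Use the same rule with the 90% threshold for EASI-90, and apply it when deriving responder status for the SAP listing.

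The cost is a short text change in each document and a few lines of code. The rule stays worst-case, so it adds no responder whose response is unproven.
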